# 2. Outcome Measures

52	2.1. Primary outcome measure:
53	The primary outcome measure is patient reported pain on a numeric rating scale (NRS) (1; no
54	pain, 10; worst pain imaginable)
55	
56	2.2. Secondary outcome measures:
57	Patient satisfaction measured on NRS scale of 1=not bad at all, to 10=worst experience
58	imaginable.
59	Analysis of risk factors associated with pain from local anaesthetic in the head and neck
60	including size of resection and injection volume:
61	• Pathology – malignant versus benign
62	Local anaesthetic volume
63	• Size of resection
64	• Site of resection
65	
66	
67	3. Methodological design
68	3.1. Study design
69	Randomized controlled trial
70	
71	3.2. Selection:
72	Patients will be selected from those attending scheduled excision of cutaneous head and neck
73	malignancies at our centre
74	
75	3.3. Inclusion criteria:

76	• Aged at least 18 years
77	• Receiving surgery to cutaneous tissues of the head and neck
78	Procedure performed under local anaesthetic
79	
80	3.4. Exclusion criteria:
81	Paediatric patients
82	• Surgery performed under general anaesthetic
83	• Mucosal operative site (e.g. oral cavity)
84	• Significant cognitive impairment (e.g. severe dementia)
85	Known sensitivity/allergy to EMLA
86	• History of a pain disorder (e.g. complex regional pain syndrome).
87	
88	3.5. Sample size calculation:
89	A formal sample size calculation will be performed after an initial pilot study of ten patients
90	per group to calculate the effect size. Other studies on using topical anaesthetic agents in
91	other non head and neck anatomical sites typically required less than 50 participants per
92	group. G*Power 3.1 (Universität Düsseldorf) software will be used to calculate the necessary
93	sample size. We will likely employ an $\alpha$ error probability of 0.05 and a power of 95%. A 10%
94	margin for safety will be used to mitigate the possible risks of participant attrition
95	
96	3.6. Randomization:
97	Computer randomization will be performed. A random number sequence will be generated
98	using randomizer.org® with numbers allocated using stratified permuted blocks of four and
99	these will be concealed in individual sealed envelopes with the aid of a research contributor.

100	Participants will be allocated in order of recruitment and in participants with more than two
101	lesions will have the more superiorly located lesion allocated first.
102	

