103	3.7. Interventions
104	Patients will be split into 4 groups:
105	• EMLA
106	Aqueous ointment
107	• Ethyl chloride spray
108	• no treatment.
109	
110	3.8. Study procedures
111	Written informed consent will be obtained prior to group allocation. Following group
112	allocation, topical agents will be administered as follows. EMLA (EMLA cream 5% 25g
113	lidocaine, 25g prilocaine) and aqueous cream will be applied to cover the surgical site,
114	delivered via an unmarked syringe to achieve single blinding. A Tegaderm® adhesive
115	dressing will then be applied over this to prevent the cream from drying out, and it will be
116	removed in the theatre before the administration of LA. The local anesthetic to be used will
117	be 1% lidocaine with 1:200,000 adrenaline and will be injected via a 25-gauge needle
118	attached to a 10ml syringe. A 5ml syringe will be occasionally used when it is not possible to
119	inject via a 10ml syringe.
120	EC will be applied to the surgical site before LA injection. The area will be sprayed at a
121	distance of 5-10cm for 4-8 seconds until the skin slightly blanches, and the fluid will be
122	allowed to evaporate.

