## 133 4. Statistical analysis

The distribution pattern of variables will be assessed using the Kolmogorov-Smirnov test. 134 The Kruskal-Wallis test and Mann Whitney test will be employed to compare groups for non-135 parametric data and for covariate analysis. The Chi-squared test will be applied to detect 136 differences for categorical data. Spearman's Rho will be used to quantify the strength of the 137 138 linear relationship between non-parametric continuous variables. A per protocol analysis will be conducted as it is believed that in cases where patients are unable to describe their pain by 139 using a number, it will disproportionately affect the results by conducting a "worst case 140 141 scenario" analysis. Furthermore, due to a minimal interval between intervention and measurement of pain outcomes in this study, there will be low rates of attrition. Statistical 142 analysis will be performed using SPSS v.26 (Aramonk, US). Statistical significance will be 143 144 considered at p < 0.05.

145

- 146
- 147
- 148

149

150	5. Miscellaneous
151	5.1. Ethical considerations:
152	This trial will be registered with the University Hospital Waterford Research and Ethics
153	Committee where full ethical approval will be obtained prior to study commencement. It
154	is considered that patient risks from this study are negligible.
155	
156	5.2. Funding:
157	No funding will be necessary for this study
158	
159	5.3. Dissemination of results
160	Results will be prepared into a scientific manuscript for publication and presented at

161 scientific surgical meetings

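### Section 4 gives no way to account for allocated arm in the risk-factor analyses; this matters mainly for injected volume, and only if volume differs by arm

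*Combined protocol and SAP*

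**What the plan says.** Section 2.2 lists as a secondary outcome "Analysis of risk factors associated with pain from local anaesthetic in the head and neck". The factors are pathology (malignant or benign), "Local anaesthetic volume", size of resection and site of resection. Allocated arm is not mentioned there.

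Section 4 is the whole analysis plan. It assigns Kruskal-Wallis and Mann-Whitney tests to non-"parametric data and for covariate analysis" and Chi-squared to categorical data. For pairs of continuous variables, Spearman's "Rho will be used to quantify the strength of the" relationship. It plans no regression, partial correlation, stratified test or within-arm analysis.

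Section 3.7 states "Patients will be split into 4 groups": EMLA, aqueous ointment, ethyl chloride spray and no treatment. The hypothesis in section 1 is that EMLA and ethyl chloride reduce the pain of injection. Section 3.8 puts consent and allocation first, then the topical agent, then the injection; the dressing over the cream is "removed in the theatre before the administration of LA". That section sets the anaesthetic solution, needle and syringe, but not the volume injected.

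**The concern.** Each named test relates pain to one factor at a time. The hypothesis says arm will lower pain in two of the four groups, so arm is a known source of variation in the outcome, and the risk-factor analysis leaves it out.

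The consequence depends on when the factor is determined.

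- **Pathology, site and probably size** are features of the lesion before allocation. Randomisation balances them on average. Omitting arm then adds the treatment effect to the noise, and chance imbalance remains, but there is no systematic bias.
- **Injected volume** is determined after allocation and after the topical agent. Randomisation does not guarantee that it is balanced. If volume differs by arm and pain differs by arm, a correlation taken over all arms mixes the relation within arms with the difference between arms.

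At stake is a published statement that larger volumes go with more pain when the topical agent accounts for both differences, or a real association that is missed.

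**Working it through.** **Inputs from the documents.** Four arms (3.7). Blocks of four (3.6), taken to imply equal allocation, which is not stated. Pain scored 1 to 10 (2.1). Significance at 0.05 (section 4), taken as two-sided. The final sample size awaits a pilot of ten per group, and section 3.5 says comparable studies usually needed fewer than 50 per group. The plan gives no figure for these analyses, so there is none to reproduce.

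**Assumptions.** 40 per arm (160 in total); pain SD 2 within arm; volume SD 1 within arm; EMLA and ethyl chloride both lower pain by 2 points or by 1 point; volume is shifted equally in those two arms.

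**Step 1: size of the distortion.** Let the pain shift be d, the volume shift v and the within-arm correlation r. Half the observations are in active arms, so the between-arm covariance is d × v / 4. The correlation over all arms is

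(2r + dv/4) / √[(4 + d²/4)(1 + v²/4)].

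- r = 0, d = −2, v = −0.5: 0.25 / √(5 × 1.0625) = 0.25 / 2.305 = 0.11.
- r = 0, d = −2, v = −0.3: 0.15 / √(5 × 1.0225) = 0.15 / 2.261 = 0.07.
- r = 0, d = −1, v = −0.5: 0.125 / √(4.25 × 1.0625) = 0.125 / 2.125 = 0.06.
- r = 0.3, d = −2, v = +0.5: (0.6 − 0.25) / 2.305 = 0.15.
- r = 0.3, d = −1, v = +0.5: (0.6 − 0.125) / 2.125 = 0.22.
- r = 0.2, v = 0: 0.4 / √5 = 0.18 for d = −2, and 0.4 / √4.25 = 0.19 for d = −1.

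So the spurious correlation is small in absolute terms, masking can be larger, and with balanced volume there is only slight shrinkage. Simulated Spearman values are a little lower in the masking cases (about 0.13 and 0.21), as expected with ranks and rounded scores.

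**Step 2: how often the test is significant.** Simulation with scores rounded and limited to 1–10. The unadjusted Spearman is set against a rank correlation with ranks centred within arm (three degrees of freedom removed).

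| Setting (40 per arm) | Unadjusted | Arm-adjusted |
|---|---|---|
| No link, volume balanced, 2-point effects | about 5% | about 5% |
| No link, volume 0.3 SD lower, 2-point | about 14% | about 5% |
| No link, volume 0.5 SD lower, 2-point | about 25% | about 5% |
| No link, volume 0.5 SD lower, 1-point | about 11% | about 5% |
| True r = 0.3, volume 0.5 SD higher, 2-point | about 40% | about 95% |
| True r = 0.3, volume 0.5 SD higher, 1-point | about 77% | about 95% |
| True r = 0.2, factor balanced, 2-point | about 57% | about 66% |
| True r = 0.2, factor balanced, 1-point | 64.5% | 66.6% |

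The last two rows are the ones that apply to factors fixed before allocation.

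**Step 3: other sample sizes and unequal effects.** Assume pain shifts of −2 (EMLA) and −1 (ethyl chloride), with volume 0.5 SD lower for EMLA and 0.25 SD lower for ethyl chloride, and no true link. The unadjusted test is significant in 7.4%, 12.3% and 17.7% of trials at 10, 25 and 49 per arm. The adjusted test stays between 4.7% and 5.3%. If volume differs but arms have equal pain, the unadjusted rate is 4.7% to 5.4%. The bias therefore needs arms to differ in both.

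**The case against.** Several objections carry weight.

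- **Pooling is not stated.** A reader might infer that the plan declares a pooled analysis. It does not. Section 4 is silent, and the named tests could be run within each arm. The point stands as the plain reading of a plan that mentions no by-arm analysis. Nor is the unit of analysis defined. Section 3.6 says that, for participants with several, "lesions will have the more superiorly located lesion allocated first", which suggests lesions but does not settle it.
- **Nothing shows that volume differs by arm.** Section 3.8 describes the injection without distinguishing arms. Timing makes a difference possible, not likely. At a shift of 0.1 SD the false-positive rate is only about 6% with 2-point effects and about 5% with 1-point effects. If only EMLA works (2 points) and volume is 0.3 SD lower there, it is about 8%. This limits the claim to a conditional one.
- **A reader might infer that all four factors are biased.** They are not. For three of them the effect is chance imbalance and lost power, which nearly vanishes with 1-point effects.
- **Adjusting for arm does not isolate a causal volume effect.** Volume may also follow resection size. Section 2.2 speaks of association, and the results should be described that way.

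What survives is that arm is recorded, is expected to change the outcome, and costs almost nothing to include.

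**Conclusion.** The concern holds in a limited form. Section 4 names unadjusted two-variable tests for the section 2.2 risk factors and does not say how allocated arm enters.

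For pathology, site and probably size, the expected cost is a modest loss of power: about 9 percentage points with 2-point effects (66 − 57) and about 2 with 1-point effects (66.6 − 64.5), at a true correlation of 0.2.

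For volume, if it differs by arm, a false association is found in about 11% to 25% of trials across the tabulated settings with unequal volume. A real association can be masked, with power of about 40% or 77% against about 95% when arm is included. If volume is balanced there is no inflation.

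The sizes rest on an assumed SD, assumed effects, assumed volume shifts and 40 per arm; the documents give none of these. The direction rests only on arms differing in both pain and volume. A reader might infer that the trial's main result is in doubt. It is not: this is a secondary analysis, and the comparison of pain between arms does not depend on it.

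**What to change.** State in section 4 that each risk-factor analysis in section 2.2 includes allocated arm. One option for all four factors is a proportional-odds model of the 1–10 score with arm as a factor. A rank-based alternative is:

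- volume and size: partial Spearman correlation given arm;
- pathology (two categories): arm-stratified Wilcoxon (van Elteren) test;
- site: an arm-stratified Kruskal-Wallis-type test or the ordinal model, since site may have more than two categories and the standard two-group van Elteren test would then not fit.

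Report injected volume by arm so that readers can see whether the condition for bias is met, and describe the findings as associations.

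The cost is a few sentences in the SAP, slightly more analysis and three degrees of freedom. No new data are needed.

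### Per protocol is the only analysis named, and the missing-score argument given for it does not justify dropping patients who gave a pain score

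*Combined protocol and SAP*

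**What the plan says.** The choice and its grounds are in Section 4 (Statistical analysis): "A per protocol analysis will be conducted as it is believed that in cases where patients are unable to describe their pain by", continuing "using a number, it will disproportionately affect the results by conducting a" worst-case analysis. A further ground is the short gap between intervention and pain rating, so that "there will be low rates of attrition".

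No other analysis population is named anywhere. There is no intention-to-treat, full-analysis, as-randomised or sensitivity analysis. The plan does not define the per-protocol set, list the deviations that would remove a patient, or say who decides on exclusions and when.

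Three other places bear on the point:

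- Section 3.8 describes masking for the two creams only ("delivered via an unmarked syringe to achieve single blinding"). The spray has its own delivery steps ("EC will be applied to the surgical site before LA injection"), and the no-treatment arm has nothing to deliver.
- Section 3.5 allows a 10% "margin for safety will be used to mitigate the possible risks of participant attrition".
- Section 3.6 says that, in patients with several lesions, "lesions will have the more superiorly located lesion allocated first". The unit allocated can therefore be a lesion, and the analysis set has to be worded for that.

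**The concern.** The reasons given do not lead to the method chosen. Rejecting worst-case imputation supports analysing the available scores by allocated arm. It does not support removing patients whose scores are available. Low attrition points the same way, because few scores would need imputing.

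In its usual meaning, per protocol drops scored patients who deviated. With no definition, those exclusions could be decided once arm and score are known. Delivery can fail in different ways by arm: cream has to cover the site and stay under a dressing until theatre, the spray has to be applied until the skin blanches slightly, and no treatment cannot fail at all. Exclusion rates could therefore differ by arm. If they do, and exclusion is related to pain, the primary comparison loses the protection of randomisation.

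This matters mainly for comparisons involving the spray or no treatment. It matters less for EMLA against aqueous cream, which share syringe, dressing, removal and single blinding.

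**Working it through.** **Text check.** Each stated reason, and whether it reaches a scored patient who deviated:

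| Reason in Section 4 | Concerns | Applies to a scored deviator? |
|---|---|---|
| Patient cannot give a number | Missing score | No |
| Worst-case analysis would distort results | Imputing a missing score | No; nothing to impute |
| Low attrition | Missing score | No |

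**Inputs for size.** The plan gives no sample size, SD or effect size (Section 3.5 defers these to a pilot), so it has no figure to reproduce. Assumed: 50 per arm; scores normal with mean 5 and SD 2.5, rounded and limited to 1–10 (realised SD 2.35); no true difference; two-sided 0.05. The 10% exclusion rate borrows the attrition margin in Section 3.5, and 20% is a stress case with no source.

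**Bias formula.** If a share q of one arm is excluded and those patients lie D points above the full arm mean, the retained mean falls by q/(1 − q) × D. With selection probability proportional to score squared, simulated D is about 1.80, 1.75 and 1.65 at 4%, 10% and 20%:

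- 4%: 0.04/0.96 × 1.80 = 0.08 points
- 10%: 0.10/0.90 × 1.75 = 0.19 points
- 20%: 0.20/0.80 × 1.65 = 0.41 points

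**Normal approximation.** Dividing each shift by 2.35 × √(1/50 + 1/n), with n = 48, 45 and 40 retained, gives z = 0.16, 0.40 and 0.83. The two-sided error, Φ(z − 1.96) + Φ(−z − 1.96), is 5.3%, 6.9% and 13.1%.

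**Simulation, 8,000 runs per case** (Monte Carlo standard error about √(0.05 × 0.95/8000) = 0.24 percentage points near 5%):

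| Exclusion | 4% | 10% | 20% |
|---|---|---|---|
| One arm, strong selection: bias (points) | −0.08 | −0.20 | −0.42 |
| Same: Mann-Whitney false positives | 5.6% | 7.2% | 13.6% |
| Same: Kruskal-Wallis, four arms | 5.2% | 6.7% | 12.0% |
| One arm, weaker selection (D about 1.0): Mann-Whitney | 4.9% | 5.4% | 7.4% |

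Across the three rates, random exclusion gives 4.6–5.2% and no bias. The same score-related exclusion in both arms gives 4.7–6.7% and no average bias. Analysis as randomised gives 4.7–5.3%. Repeat runs with strong selection gave 4.5–5.9% at 4% excluded, 7.0–7.3% at 10% and 13.0–14.1% at 20%. The 4% case is therefore indistinguishable from nominal.

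**Cost of analysing as randomised.** Assume delivered treatment lowers pain by 1.5 points (1.33 after rounding and limiting to 1–10) and a share q of that arm gets no benefit, unrelated to pain. The expected difference is (1 − q) × 1.33: 1.28, 1.20 and 1.06 at 4%, 10% and 20%. Simulated values (5,000 runs) are 1.27, 1.20 and 1.07. Power at 50 per arm is 77%, 73% and 62% as randomised, against 80%, 80% and 77% per protocol.

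**The case against.** The strongest reply is that the plan never says scored deviators will be dropped. Per protocol is set against a worst-case analysis for patients who cannot give a number, so the authors may mean only complete cases by allocated arm. On that reading the defect is an undefined term and the bias argument falls away. This stands as a possible reading, but nothing in the plan fixes it, and it is not the usual meaning of the term.

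The harm also needs several things together: deviations, exclusion of scored deviators, a link with pain, and imbalance between arms. The plan establishes none of them. This stands too, and at low exclusion rates the effect is negligible. The low rate the plan expects, however, is for attrition; it gives no rate for deviations. For the same reason the 10% figure above is only a borrowed illustration.

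Finally, patients who cannot give a number stay out of the analysis under the fix, so any selection from that source remains. That is true, and it is why missing scores should be reported by arm. It is no reason to exclude scored patients as well.

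**Conclusion.** The concern holds. Per protocol is the only analysis named, its justification covers missing scores only, and the set is undefined. That much is certain from the text.

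The consequence is conditional. If exclusion is score-related and confined to one arm, the false-positive rate under the assumptions above is close to nominal at 4% excluded, about 7% at 10% and about 14% at 20%, with bias up to about 0.4 points on the 1–10 scale. If exclusions are unrelated to pain, or equally related in both arms, there is no average bias. The documents do not allow the direction to be predicted. With few exclusions the effect is small, but the plan's reasoning does not support the method it names, and correcting it is cheap.

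**What to change.** Replace the per-protocol sentence in Section 4 with:

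> The primary analysis includes every randomised patient (or lesion) with a recorded NRS score, in the arm allocated, whatever treatment was delivered. Missing scores are not imputed as worst case and are reported by arm. A per-protocol analysis, with qualifying deviations defined in advance, is supportive only.

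This keeps the authors' objection to worst-case imputation. It needs no extra patients, procedures or data. The price is dilution if deviations are common: in the illustration, a loss of 3, 7 and 15 percentage points of power at 4%, 10% and 20% non-delivery (80 − 77, 80 − 73, 77 − 62). If the authors already meant complete cases by allocated arm, the change only makes that explicit.

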### 126 **3.9.**Assessing outcomes

The key focus in this study will be the assessment of pain linked to the injection of local anesthesia (LA). Following the LA administration, each participant will be prompted to evaluate the pain they undergo using a numeric rating scale (NRS; 1=no pain, 10=worst pain imaginable). Subsequent to the procedure, patients will be inquired about their overall perception of the experience (1=not bad at all, 10=worst experience imaginable).

132

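### No entry criterion requires that a patient can give a 1–10 pain score, yet section 4 makes inability to do so its reason for a per-protocol analysis

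*Combined protocol and SAP*

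**What the plan says.** Section 2.1 makes the primary outcome a pain score from 1 to 10, stated by the patient. Section 3.3 sets three conditions: adult age, the type of surgery ("Receiving surgery to cutaneous tissues of the head and neck") and local anaesthetic. None concerns ability to use the scale. The nearest exclusion, in section 3.4, is "Significant cognitive impairment (e.g. severe dementia"), where dementia is an example.

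On timing, section 3.8 states: "Written informed consent will be obtained prior to group allocation". The first use of the scale that the plan describes is in section 3.9: "Following the LA administration, each participant will be prompted to evaluate the pain they undergo using a numeric rating scale".

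Section 4 chooses a per-protocol analysis and gives this reason: "in cases where patients are unable to describe their pain by" "using a number, it will disproportionately affect the results by conducting a" worst-case analysis. It adds that, given the short gap between intervention and "measurement of pain outcomes in this study, there will be low rates of attrition". Section 3.5 allows a 10% margin for attrition.

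**The concern.** The plan recognises that some enrolled patients may be unable to supply the primary outcome, and it deals with this at the analysis, after allocation. Yet inability to use a numeric scale is often present before treatment and could be found before the envelope is opened.

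Three things are at stake. Places are randomized and then not used. The judgement that a patient cannot give a number is made when staff can know the arm: section 3.8 describes single blinding for the two creams, and spray or no treatment is evident to whoever delivers it. And with no rating before allocation, the data do not show whether a patient without a score could ever use the scale or was unable to answer because of the injection. These two kinds of missing score mean different things for the comparison.

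**Working it through.** The plan gives no sample size, standard deviation, effect size or non-response rate, so there is no figure to reproduce. The check is mainly a reading of the sections in the order in which a patient meets them.

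**1. Order of events.** Eligibility (3.3, 3.4) has no test of the scale. Consent follows (3.8), then allocation and topical treatment (3.8), the injection, and the described rating (3.9). Section 4 then applies. A patient who cannot give a number passes every stage before the rating. A contact point before allocation exists and is not used for this purpose.

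**2. What section 4 does with such patients.** It rejects a worst-case score and adopts a per-protocol analysis. The term is not otherwise defined, so removal from the primary analysis is an inference, though the natural one.

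**3. Two kinds of missing score.**
- *Inability present before allocation.* It should be about equally frequent in each arm. Leaving these patients out restricts the population and costs numbers, but in expectation does not bias the comparison, provided that the decision is not influenced by the arm. A check at consent would find most of them.
- *Non-response caused by the injection.* It can depend on the arm and so can bias the comparison. A check at consent does not prevent it, but shows that the patient could use the scale beforehand.

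**4. Cost in power (illustration only).** Assumptions: two-sided 0.05 (section 3.5 gives 0.05 without sidedness), one pairwise comparison of means by normal approximation, 95% power (3.5), and 50 analysable per group. The 50 is the upper end of what section 3.5 reports for other studies; it is not this trial's size.

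Standardized difference giving 95% power at 50 per group: d = √(2/50) × (1.960 + 1.645) = 0.2 × 3.605 = 0.721.

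Power with n analysable per group: Φ(d√(n/2) − 1.960).

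| Scores lost | 50 randomized per group | 55 randomized per group (10% added) |
|---|---|---|
| 0% | 95.0% | 96.6% |
| 5% | 94.0% | 95.8% |
| 10% | 92.8% | 94.8% |
| 20% | 89.7% | 92.2% |

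For example, 10% lost from 55 leaves 49.5, and Φ(0.721 × √24.75 − 1.960) = Φ(1.627) = 94.8%. The margin roughly covers the power cost up to 10% loss. It does nothing about which patients are removed.

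**5. Chance of meeting the problem in the pilot.** Ten per group in four groups is 40 patients. The chance that at least one gives no number is 1 − (1 − p)^40. At assumed rates p of 2%, 5% and 10% this is 55%, 87% and 99%. Even a low rate would probably raise the question in the pilot that is to supply the effect size.

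**The case against.** The strongest objection is that the harm and the remedy do not match. Loss that depends on the arm comes from patients distressed by the injection. They would give a rating at consent, be randomized and still be missing. The patients whom the check removes are largely those whose loss does not depend on the arm. This stands, and it limits the claim: the check cannot be presented as a cure for bias.

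Four further points are fair in part.
- Section 4 speaks conditionally and predicts little attrition. A reader might infer that the plan expects many such patients, or that the background describes an elderly trial population. It does neither: it gives no frequency, and section 1 names advanced age only as a risk factor for these lesions. However, the prediction rests on the short interval to measurement, which has no bearing on inability to use a number.
- The cognitive exclusion and written consent already screen out some patients. Lesser impairment and other reasons for inability remain eligible, and section 4 still allows for such cases.
- Staff could record why a score is missing. Nothing prevents this, but the plan does not ask for it, and a reason given afterwards is weaker evidence than a rating obtained beforehand.
- Pain at rest may often be 1, so the question tests the scale only lightly and may add little as a baseline value. That is so; its purpose is to show that the patient can answer with a number.

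**Conclusion.** The point holds as a modest, inexpensive improvement. The plan admits patients who may be unable to supply its primary outcome and, on the natural reading of an undefined per-protocol analysis, drops them after randomization for a reason that could largely be settled before it.

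A reader might go further and infer that the treatment comparison is biased by a stated number of pain points, or that the check would remove the problem at its source. The documents support neither. They give no non-response rate, no arm means and no split between the two kinds of missing score, so any size of bias would rest entirely on assumed inputs, and injection-related non-response would remain. Lost power is secondary: under the assumptions shown, the 10% margin absorbs most of it up to 10% loss. The benefit is fewer avoidable exclusions, fewer decisions taken when the arm can be known, and missing scores that can be interpreted.

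**What to change.** - **Sections 3.3 and 3.8:** add ability to give a rating on the trial's 1–10 scale as an entry condition. Ask for the rating after consent and before the envelope is opened, and record it. Do not randomize a patient who cannot give a number; count such patients.
- **Section 4:** state that inability to use a number is handled at entry and is no longer a ground for dropping randomized patients. Analyse all randomized patients who give a score in the arm to which they were allocated. Report every score still missing after allocation by arm, with its reason.

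The cost is one question, one line in the criteria and a short rewrite of section 4. The downside is that patients who cannot use a numeric scale are not enrolled, so the result does not cover them. On the natural reading, the present plan leaves them out of the primary analysis anyway.

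### The plan calls patient risk negligible but provides for no recording or by-arm reporting of adverse reactions, so the trial could recommend an agent with no count of harms in any arm

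*Combined protocol and SAP*

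**What the plan says.** **Risk.** Section 5.1 states that it "is considered that patient risks from this study are negligible". No data or reasoning accompany the statement.

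**Outcomes.** Section 2.1 makes patient-reported pain on a 1–10 scale the primary outcome. Section 2.2 adds a satisfaction score, also 1–10, and an analysis of factors associated with pain (pathology, anaesthetic volume, size and site of resection).

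**Assessments.** Section 3.9 has two. The first is the pain score: "Following the LA administration, each participant will be prompted to evaluate the pain they undergo using a numeric rating scale". The second is the experience score: "Subsequent to the procedure, patients will be inquired about their overall perception of the experience".

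**Exposure.** Section 3.4 excludes patients with "Known sensitivity/allergy to EMLA". Under section 3.8 the two creams are covered with an adhesive dressing, which comes off in theatre before the injection, and ethyl chloride is sprayed until the skin blanches slightly. The injected local anaesthetic is to "be 1% lidocaine with 1:200,000 adrenaline and will be injected via a 25-gauge needle".

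**Analysis.** Section 4 names a chi-squared test for categorical data but ties it to no safety variable.

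**The concern.** The plan treats at least one hazard as real enough to exclude patients for it. Excluding a known allergy cannot catch a first reaction, and no matching exclusion is listed for ethyl chloride or aqueous cream. Even so, no adverse-event definition, skin check, recording field, reporting route or safety analysis appears in the text.

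The trial compares two active agents with an inert cream and with no treatment, and section 5.3 intends publication. A paper written from the planned data could say that an agent reduces injection pain and is worth using, while giving no count of reactions in any arm. The statement about risk in 5.1 would remain a premise that the trial never examined.

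Timing adds to this. After the dressing is removed, or the spray has evaporated, the same site is injected with lidocaine and adrenaline and then operated on. A local reaction is easiest to read before those steps, and the plan specifies no look at the skin then.

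**Working it through.** The plan gives no safety figure, event rate or final sample size, so there is no figure of its own to reproduce. The check has two parts.

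**1. Is harm recorded at any planned step?**

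| Step | Arms | Recorded under the plan | Skin reaction or adverse effect recorded? |
|---|---|---|---|
| Cream and dressing applied (3.8) | EMLA, aqueous | Nothing specified | No |
| Dressing removed in theatre (3.8) | EMLA, aqueous | Nothing specified | No |
| Spray applied and evaporates (3.8) | Ethyl chloride | Nothing specified | No |
| After the injection (3.9) | All four | Pain, 1–10 | No |
| After the procedure (3.9) | All four | Overall experience, 1–10 | No |

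The experience score reflects topical agent, injection and surgery together. It cannot separate a skin reaction from a difficult excision. Section 3.6 also provides for allocating a participant's lesions in sequence, so one patient may have lesions in different arms. A single score for that patient cannot be tied to one agent.

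**2. What could recording show at plausible sizes?**

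Inputs: 10 per group is the pilot size in 3.5, taken here as one lesion per patient. For the main phase I assume 50 per group, or 49 for the comparison of two arms. Section 3.5 says only that studies at other anatomical sites typically needed fewer than 50 per group, so neither figure is this trial's size. All event rates are assumptions, and lesions are treated as independent.

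*Upper limit with zero events*, one-sided 95%, exact: 1 − 0.05^(1/n).
- n = 10: 1 − 0.05^(1/10) = 0.259, or 25.9%.
- n = 50: 1 − 0.05^(1/50) = 0.058, or 5.8%.

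*Chance of at least one event in an arm*: 1 − (1 − p)^n.

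| True rate p | n = 10 | n = 50 |
|---|---|---|
| 1% | 9.6% | 39.5% |
| 2% | 18.3% | 63.6% |
| 5% | 40.1% | 92.3% |
| 10% | 65.1% | 99.5% |

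*Power to compare two arms*, two-sided 0.05, 49 per arm, normal approximation: Φ((|p₁ − p₂| − 1.96·SE₀)/SE₁), where SE₀ uses the pooled rate and SE₁ the separate rates.
- 5% against 1%: (0.04 − 1.96 × 0.0345)/0.0342 = −0.81, power 21%.
- 10% against 2%: (0.08 − 1.96 × 0.0480)/0.0473 = −0.30, power 38%.
- 20% against 2%: (0.18 − 1.96 × 0.0632)/0.0605 = 0.93, power 82%.

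At these sizes recording would probably reveal a common reaction. It could not exclude a rare one, and a formal comparison would detect only large differences. That supports descriptive reporting with confidence limits rather than a hypothesis test.

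**The case against.** **Risk as an ethics judgement.** The statement in 5.1 is made in advance and is not a hypothesis under test. Zero-event limits of this width would apply to any trial of these sizes, whether or not harm is recorded. This stands: the limits illustrate what counts could show and do not measure the defect. The defect is that no counts exist.

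**Can the trial never show harm?** A reader might infer this, but the documents do not support it. Both scores can be worse on an active agent, so part of tolerability is measured. The plan is silent on clinical records and ethics-committee conditions, and nothing in it forbids ad hoc reporting.

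**Is the time before injection the only usable interval?** A reader might infer this as well, and the documents do not say it. All four arms receive the same injection and surgery, so an excess over aqueous cream or no treatment could be attributed by randomisation even afterwards, with low power, provided events were recorded. Reactions may also be delayed or systemic, or lie in skin around the site. What stands is that the moment before injection is the cleanest for a local check.

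**Practical limits on a remedy.** Only the cream arms have a dressing, so a check tied to its removal would miss two arms. Slight blanching is the intended endpoint of the spray; counting it would bias the comparison against that arm. An inspection that delays the injection could alter the intervention. A per-patient question cannot be assigned to an arm when a patient's lesions differ in allocation. A review of harm counts after the pilot would have no criterion, and at 10 per arm only a 9.6% chance of seeing any event at a true rate of 1%. All of these stand, and they shape the fix.

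**Conclusion.** The concern holds as a gap in data collection. The plan asserts low risk without a basis and provides for no collection or by-arm reporting of adverse reactions, and analysis after the event cannot repair that. It should be corrected before enrolment. The validity of the pain comparison is untouched; what is incomplete is any conclusion that weighs benefit against harm.

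The size of the gap cannot be stated as a rate, because the plan gives neither a final sample size nor an event rate. The upper limits of 25.9% and 5.8% rest on 10 and an assumed 50 independent lesions per arm with no events. The conclusion rests on the supplied text; nothing is inferred from removed pages.

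**What to change.** 1. **Section 3.9, before injection.** The person giving the local anaesthetic injection, who is present in all four arms, notes for each lesion immediately beforehand any skin reaction on a short fixed list. Define the slight blanching intended by the spray in 3.8 as expected and do not count it. The note must not lengthen the interval before injection, and the finding must not be voiced before the pain score is given.
2. **Section 3.9, after the procedure.** At the existing contact, record any unwanted effect, by lesion where it is local. Report systemic effects separately for patients whose lesions are in different arms.
3. **Section 2.2.** Add *local reaction or adverse event, by arm* as a descriptive safety outcome: counts with exact confidence limits, allowing for several lesions in one patient.
4. **Section 5.1.** Replace *negligible* with *expected to be low; recorded by arm*.

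**Cost.** A short amendment and about one extra line on the data sheet, with no additional visits or patients. A visible skin change may hint at the allocation, so a slight unblinding risk remains. Effects that appear after the post-procedure contact would still be missed unless a later contact were added.
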